## 9.0 STATISTICAL CONSIDERATIONS

9.1 PRIMARY ENDPOINT – The primary endpoint of this trial is the level of IRS-1/PI3K/AKT pathway activation in primary tumors, measured by densitometric analysis of immunoblot signals of markers of pathway activation (IRS-1, phospho-IRS-1-Ser636/639, phospho-AKT-T308, phospho-AKT-S473).

9.2 SECONDARY ENDPOINT – The secondary endpoint is Ki67 score, as determined by the percentage of Ki67+ tumor cells by IHC.

9.3 PRIMARY ANALYSIS PLAN - The primary analyses determine whether RAD001 treatment of tumor samples *ex vivo*, and/or presurgical treatment of patients with Letrozole, alter IRS-1/PI3K/AKT pathway activation in breast tumors. Signal values of IRS-1, phospho-IRS-1-Ser636/639, phospho-AKT-T308, phospho-AKT-S473 will be determined by densitometric analysis of immunoblots. Below is an illustration of projected data and relevant comparisons. Signal values of control (DMSO)-treated and RAD001-treated tumor samples will be compared using a 2-sided paired t-test. These tests will be performed separately in tumors from each arm of the study (*i.e.*, untreated, or letrozole-treated, as shown below in *left* and *center* panels). An additional test will compare the magnitude of change in signal values in Arm A vs. Arm B (2-sided independent t-test), to determine whether Letrozole treatment alters response to RAD001 (shown below in *right* panel).

9.4 SECONDARY ANALYSIS PLAN – Secondary analysis to determine whether presurgical treatment with Letrozole suppresses IRS-1/PI3K/AKT activation compared to baseline will be achieved using a paired t-test comparing IRS-1/PI3K/AKT pathway markers scored by IHC analysis of matching tumor samples from patients acquired A) at baseline (diagnostic biopsy) and B) at surgery (post-Letrozole). We will also determine whether tumor Ki67 IHC score is associated with the level of IRS-1/PI3K/AKT pathway activation, or with RAD001-induced changes in IRS-1/PI3K/AKT signaling, by Spearman correlation between Ki67 score and densitometric signal values of pathway markers as determined by immunoblot analysis or IHC Histoscore.

9.5 STATISTICAL TESTING - All statistical tests will be 2-sided, and the overall type I error will be 0.05.

9.6 SAMPLE SIZE – The primary analyses determine whether RAD001 treatment of tumor samples *ex vivo*, and/or presurgical treatment of patients with Letrozole,

alter IRS-1/PI3K/AKT pathway activation in breast tumors. RAD001-induced pathway activation will be defined as a  $\geq 50\%$  increase in phospho-AKT densitometric signal value compared to DMSO-treated control; this scoring system provides a binary metric for sample size determination for Arm B (below). Given that this is a pilot study, we do not know what fraction of ER+/HER2-breast tumors will exhibit RAD001-induced IRS-1/PI3K/AKT activation. Hence, tumors from 10 untreated patients in Arm A will be used to determine the frequency with which RAD001 induces AKT activation.

The fraction of tumors in Arm A (untreated patients) that exhibit RAD001-induced AKT activation will be used to determine the number of patients that need to be enrolled in Arm B (presurgical Letrozole treatment) to detect a significant effect of presurgical Letrozole treatment on RAD001-induced AKT activation. We estimate that  $\leq 15\%$  of Letrozole-treated tumors will exhibit RAD001-induced AKT activation. If we observe that RAD001 increases phospho-AKT in X of 10 tumors in Arm A, we will enroll Y patients in Arm B (presurgical Letrozole) to provide a sufficient number of tumors to detect a significant effect ( $p \leq 0.05$ ) of presurgical Letrozole on RAD001-induced changes in phospho-AKT levels with 80% power (calculated using uncorrected chi-squared statistic). If we observe that  $\leq 3$  tumors from untreated patients in Arm A exhibit RAD001-induced AKT activation, the study will be terminated at this point, and Arm B will not enroll patients. To account for interpatient/intertumor variability, we will enroll a minimum of 10 patients in Arm B.

X (n of tumors from untreated patients that exhibit a <math>\geq 50\%</math> increase in P-AKT levels in response to RAD001 treatment ex vivo)	Y (n of patients to be enrolled in Arm B, presurgical Letrozole)
0-3	Terminate study
4-6	30
7-8	14
9-10	10

- 10.

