### 1.6. Study rationale

We propose a presurgical study in patients with Stage I-III ER+/HER2- breast cancer to determine whether anti-estrogen therapy (Letrozole) suppresses mTORC1 inhibitor (RAD001)-induced activation of PI3K/AKT signaling. As the primary objective is to determine whether anti-estrogen therapy alters mTORC1 inhibitor-induced signaling that can be assessed in a short time frame *ex vivo*, we will treat patients with or without Letrozole for 10-21 days prior to surgery; this time frame will allow sufficient time for maximal estrogen suppression and downstream changes in the levels of ER-regulated transcripts and encoded

proteins. Viable core samples of surgically resected tumors will be used for *ex vivo* culture to assess the effects of RAD001 on signaling, to avoid exposing subjects to potentially adverse side effects of RAD001. Findings from this study will provide mechanistic insight into the effects of mTORC1 and ER inhibition on oncogenic signaling pathways in cancer cells.

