## 2.0 OBJECTIVES

### 2.1 Primary Objectives

1. Arm A: To determine whether mTORC1 inhibition with RAD001 increases IRS-1/PI3K/AKT pathway activation in ER+/HER2- breast tumors *ex vivo*.
2. Arm B (comparison with Arm A): To determine whether presurgical treatment of patients with ER+/HER2- breast cancer with Letrozole suppresses IRS-1/PI3K/AKT pathway activation compared to tumors from untreated patients.

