**5.5.2. Immunohistochemical analysis of pre- vs. post-Letrozole tumors.**  
Baseline (diagnostic core biopsy specimen) and post-Letrozole (surgical specimen) tumor samples will be sectioned and processed for IHC in the Pathology Translational Research Shared Resource. Tissue sections will be immunostained using antibodies against ER, PR, and Ki67. ER and PR

will be scored using a Histoscore scale (23); we expect Letrozole treatment to decrease PR levels, while ER may be unaffected. Ki67 will be scored by counting the number of positively-stained cells in 10 high-power (400x magnification) microscopic fields (24, 25). Pre- and post-Letrozole Ki67+ cell counts will be compared by t-test; Letrozole treatment should induce an overall decrease in Ki67 score.

The primary goal of this analysis is to determine whether changes in signaling induced by RAD001 treatment *ex vivo* are associated with Ki67 score. A higher post-anti-estrogen Ki67 score, and a smaller decrease in Ki67 score in response to presurgical treatment with an anti-estrogen, are associated with shorter recurrence-free survival (26). Hence, it is thought that a higher level of residual tumor cell proliferation (higher Ki67 score) following anti-estrogen treatment, or a weaker biological response (change in Ki67 score) to anti-estrogen treatment, are indicative of less dependence of tumor cells on ER for growth and survival. Our preclinical data indicate that ER drives IRS-1 and IGF-1R expression, which facilitate RAD001-induced PI3K/AKT activation. Therefore, in tumors that are less dependent upon ER, Letrozole treatment is expected to have less of an effect on IRS-1/PI3K/AKT signaling. Such findings would support the use of combinations of anti-estrogens and mTORC1 inhibitors in patients with ER-driven tumors.

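### The 80% power in Section 9.6 belongs to a responder chi-squared test that no analysis section lists, and varies from 39% to 97% over X=4 to 9; the planned between-arm t-test has no stated power and, in the text, no scale

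*Combined protocol and SAP*

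**What the plan says.** Section 9.3 (Primary Analysis Plan) lists paired t-tests of DMSO against RAD001 signal within each arm, then one between-arm test: "An additional test will compare the magnitude of change in signal values in Arm A vs. Arm B (2-sided independent t-test". Its stated purpose is "to determine whether Letrozole treatment alters response to RAD001". The text gives no effect size, SD or power for it and does not say whether change is a difference, a percentage or a ratio. It points to an illustration whose right panel shows this comparison.

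Section 9.6 (Sample Size) works on another quantity. A tumor counts as activated if it shows a rise of at least 50%, defined as an "increase in phospho-AKT densitometric signal value compared to DMSO-treated control". On this score 9.6 says "this scoring system provides a binary metric for sample size determination for Arm B". Arm A has 10 tumors, X of them activated; at most 15% of Letrozole-treated tumors are expected to be activated. Arm B then enrolls Y=30 (X=4-6), 14 (X=7-8) or 10 (X=9-10), which is said to detect the Letrozole effect "with 80% power (calculated using uncorrected chi-squared statistic".

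The other planned analyses are a paired t-test and Spearman correlations (9.4) and a Ki67 comparison (5.5.2: "Pre- and post-Letrozole Ki67+ cell counts will be compared by t-test"). Section 9.5 sets an overall two-sided type I error of 0.05; 9.1 names four markers.

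**The concern.** A reader of 9.6 will take 80% as the power of the planned Arm A versus Arm B comparison. It is the power of a different test on a different variable. Nothing says what difference the t-test could detect.

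The scale matters because the two sections may not mean the same thing by change. Section 9.6 measures response relative to each tumor's own DMSO control. The text of 9.3 speaks of change in signal values, which could be read as a plain difference. If Letrozole lowers the control signal, the same fold response gives a smaller absolute difference, and the test could report an altered RAD001 response that is only a lower starting level. Section 1.4 makes a lower level plausible for IRS-1, whose mRNA fell after Letrozole in the cited profiling study. For phospho-AKT it is only a hypothesis (Section 2.2, objective 1).

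**Working it through.** **1. Reproduce the 80%.** Inputs from 9.6: Arm A n=10 with rate p_A=X/10 taken as true; Arm B n=Y with p_B=0.15; uncorrected chi-squared, two-sided 0.05 (9.5). With p̄ the pooled rate,

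power = Φ{[(p_A − p_B) − 1.96·√(p̄(1−p̄)(1/10+1/Y))] / √(p_A(1−p_A)/10 + p_B(1−p_B)/Y)}.

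- X=6, Y=30: p̄=0.2625; (0.45 − 1.96×0.1607)/0.1681 = 0.80, so 79%.
- X=7, Y=14: p̄=0.3792; (0.55 − 1.96×0.2009)/0.1735 = 0.90, so 82%.
- X=4, Y=30: p̄=0.2125; (0.25 − 1.96×0.1494)/0.1681 = −0.25, so 40%.

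The 80% therefore is a two-proportion figure, met closely at X=6 and X=7. Exact power, summing binomial probabilities over every outcome that the chi-squared test rejects:

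| X | Y | Exact power |
|---|---|---|
| 4 | 30 | 39% |
| 5 | 30 | 61% |
| 6 | 30 | 80% |
| 7 | 14 | 81% |
| 8 | 14 | 93% |
| 9 | 10 | 97% |

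At X=10 it is practically 100%. With Arm A held at 10, the formula's limit for an unlimited Arm B is 57% at X=4 and 79% at X=5, so no value of Y would reach 80% in those rows.

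**2. Is the t-test weaker?** Assume log-ratios are normal with equal SD in both arms and produce the same responder rates. The standardized difference is d = Φ⁻¹(X/10) − Φ⁻¹(0.15); at X=4, d = −0.25 + 1.04 = 0.78. Pooled t-test power with fixed n is 55%, 79%, 93% and 95% at X=4, 5, 6 and 7, against 39%, 61%, 80% and 81% for the responder test. Under this model it is stronger.

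**3. What the t-test can detect.** The documents give no SD, so only SD units are possible. Noncentral t, two-sided 0.05, 80% power, one marker, Arm A n=10, fixed Arm B n: 1.32, 1.21 and 1.05 SD at Arm B n=10, 14 and 30 (pooled); 1.33, 1.23 and 1.09 SD (Welch). If 0.05 were split equally over four markers (assumed, 0.0125 each), the pooled figures become 1.64, 1.49 and 1.27 SD.

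**4. These are not power within a row of the table.** Y is chosen from the same Arm A tumors that enter the t-test. Simulated with Arm A at 2-fold, log SD 0.3 and the 1.5-fold cut (all but the cut assumed), Welch power at 1.33, 1.23 and 1.09 SD is 93%, 72% and 21% in the n=10, 14 and 30 branches.

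**5. Scale.** Assume the same true 2-fold response in both arms, log-fold SD 0.3, between-tumor log SD of control signal 0.3 to 1.0, and fixed Arm B n of 10 or 14. Change on the absolute scale is control × (fold − 1). Rejection rate at nominal 5%:

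| Control signal in Arm B | Absolute, Welch | Absolute, pooled | Log ratio |
|---|---|---|---|
| 25% lower | 3-12% | 5-17% | about 5% |
| Halved | 10-52% | 13-64% | about 5% |

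The high ends belong to the smallest between-tumor SD. With a weaker response (1.5-fold, log-fold SD 0.4, n=10 to 30) the Welch figures are 3-6% and 4-16%.

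**The case against.** Section 9.6 openly calls the binary score a sizing metric and the study a pilot. Sizing on a dichotomized outcome and analyzing the continuous one is conservative under the model in step 2. That stands: a reader might infer that the t-test is underpowered, and the documents do not support it.

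A reader might also infer that the responder test will never be run. That is too strong. Section 9.6 defines activation, counts it in Arm A, uses it to decide whether Arm B opens, and speaks of detecting a significant effect on it. A comparison may be implied. What can be said is that no analysis section lists it.

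The scale harm is conditional. The right panel may already show a relative axis, the only explicit scale in the text (9.6) is relative, and the large error rates need an assumed halving of control signal. With a 25% drop the effect is small. So a missing statement is established, not a biased analysis.

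Finally, it would be tempting to replace the 80% with one detectable difference per row. Step 4 shows why that would be another unqualified figure.

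**Conclusion.** The point holds in a limited form, at minor to moderate severity. The 80% is not the power of the planned between-arm test, and as a blanket figure it fails for its own test at X=4 and X=5 (39% and 61%); it is about met at X=6 and 7 and exceeded from X=8. These values rest on 15% responders in Arm B and on X/10 being the true Arm A rate. The planned t-test lacks an effect size, SD, power and, in the text, a scale. Step 2's advantage for the t-test rests on normal log-ratios, equal SDs and fixed n.

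Two matters are secondary. The choice between Welch and pooled is open, since either is an independent t-test. Objective 2 also has two readings: Section 2.1 asks whether treatment "with Letrozole suppresses IRS-1/PI3K/AKT pathway activation compared to tumors from untreated patients", while Section 1.6 asks whether it "suppresses mTORC1 inhibitor (RAD001)-induced activation of PI3K/AKT signaling". Only the second has a between-arm test in 9.3.

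**What to change.** 1. In 9.3, state in words that change is log(RAD001/DMSO) per tumor, or the relative scale that the illustration already shows, and use it in the between-arm t-test.
2. In 9.6, say that the 80% refers to the responder chi-squared used for sizing, and replace the blanket figure with its power by X (39% to 97% over X=4 to 9). Either list that comparison in 9.3 or say that it is for sizing only.
3. If a detectable difference is quoted for the t-test, label it as a fixed-n, single-marker figure at two-sided 0.05: 1.32, 1.21 and 1.05 SD (pooled) at Arm B n=10, 14 and 30. Add that it is not the power within each X branch, because Arm B size depends on the same Arm A data, and that it does not allow for the overall 0.05 across four markers in 9.5.

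If space allows, reconcile the two readings of objective 2.

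The cost is wording. No patients, tissue or blots are added, and the X-to-Y table can stay. The downside is that the stated power looks less favorable in the X=4 and X=5 rows.

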### 2.2 Secondary objectives

1. To determine whether presurgical treatment with Letrozole suppresses IRS-1/PI3K/AKT pathway activation compared to baseline.
2. To determine whether the level of IRS-1/PI3K/AKT pathway activation is correlated with rate of tumor cell proliferation as determined by Ki67 score.
3. To determine whether RAD001-induced changes in IRS-1/PI3K/AKT signaling *ex vivo* are correlated with rate of tumor cell proliferation as determined by Ki67 score.
4. To identify changes in mRNA levels of ER-regulated gene induced by presurgical treatment with Letrozole.

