## 3.0 ELIGIBILITY CRITERIA

### **Inclusion Criteria:**

- 3.1. Histologic documentation of invasive breast cancer by core needle or incisional biopsy. Excess baseline biopsy tumor tissue sufficient to make three 5-micron sections must be available for molecular analyses as part of this study.
- 3.2. The invasive cancer must be estrogen receptor alpha (ER)-positive, with ER staining present in greater than 50% of invasive cancer cells by IHC
- 3.3. The invasive cancer must be HER2-negative (IHC 0-1+, or with a FISH ratio of <1.8 if IHC is 2+ or if IHC has not been done).
- 3.4. Clinical Stage I-III invasive breast cancer with the intent to treat with surgical resection of the primary tumor. Tumor must be  $\geq 2$  cm to provide adequate tissue.

- 3.5 Patients with multicentric or bilateral disease are eligible if the target lesions meet the other eligibility criteria. Samples from all available tumors are requested for research purposes.
- 3.6. Women  $\geq$  age 18, for whom adjuvant treatment with an aromatase inhibitor would be clinically indicated. Women must be either post-menopausal, or pre-menopausal having undergone oophorectomy.
- 3.7. Patients must meet the following clinical laboratory criteria:
  - Absolute neutrophil count (ANC)  $\geq$  1,000/mm^3 and platelet count  $\geq$  75,000/mm^3.
  - Total bilirubin  $\leq$  1.5  $\times$  the upper limit of the normal range (ULN).
  - Alanine aminotransferase (ALT) and aspartate aminotransferase (AST)  $\leq$  3  $\times$  ULN.
- 3.8. Ability to give informed consent.

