#### 5.2.1. *Surgery and tumor specimens*

The patient will undergo definitive surgical resection of the primary tumor.

Management of the axilla will be left to the judgment of the surgical oncologist and the patient.

It is strongly preferred that surgery be scheduled between Monday and Thursday for optimal timing of tissue fixation and processing.

The Pathologist will promptly dissect the surgical primary tumor specimen. ASCO-CAP guidelines require initiation of dissection of a surgical specimen within 1 hour of removal from the patient; for this study, minimal “cold ischemia time” is preferred.

The Pathologist will assess whether the tumor specimen is large enough to procure:

- A. tissue for routine diagnostics
- B.  $\geq 8$  core punch biopsies that are 1 mm in diameter and  $\geq 0.5$  cm long for research

C.  $\geq 4$  core punch biopsies that are 3 mm in diameter and  $\geq 0.25$  cm long for research

A 2-cm tumor is expected to provide sufficient material for all needs.

When the tumor is sufficiently large to provide adequate tissue (e.g.,  $>3$  cm), the Pathologist will first remove core punch biopsies for this research study using 1-mm and 3-mm punch biopsy devices. **All research samples must be acquired within 1.5 hours of tissue removal from the patient; a shorter lag time is strongly preferred to maximize tissue viability.** The Pathologist will then acquire tissue samples for routine diagnostics.

If the tumor specimen is approximately 2 cm, the Pathologist may opt to first procure tissue for routine diagnostics. Then if adequate tumor tissue remains to provide punch biopsies for research purposes, these samples will be taken from the tumor. If the tumor is too small to provide adequate tissue for research, the tumor will be considered non-evaluable and the patient will need to be replaced.

Punch biopsy tumor specimens required for this research study are listed below in order of priority.

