**A) Fresh tissue (n=8)** - Using a **1-mm** punch biopsy device with plunger (provided by [name]), remove 8 tumor samples  $\geq 0.5$  cm long. These samples will be **immediately** placed into cold (0-4°C) tissue culture medium (serum-free DMEM + Pen/Strep; provided by [name] to be kept on-hand in Pathology lab) and kept on ice or refrigerated (0-4°C). These tissues will be transported **within 30 minutes** of dissection to [name] lab on the 6th floor of Rubin Research Building. [name], [name], and [name] (members of the [name] lab) will be responsible for transporting tissues, and need to be contacted early on the date of surgery with notification that samples will be available the same day. They will be paged when tumor tissues are available for pick-up.

**B) Frozen tissue (n=2)** - Using a **3-mm** punch biopsy device with plunger (provided by [name]), remove 2 tumor samples  $\geq 0.25$  cm long, put into cryotubes (1 core per tube), and snap-freeze in liquid nitrogen. Liquid nitrogen can be provided in a small container by the [name] lab, if they are notified early on the day of surgery.

**C) Formalin-fixed (FFPE) tissue (n=2)** - Using the same **3-mm** punch biopsy device, remove 2 tumor samples  $\geq 0.25$  cm long, fix in formalin (3 hours to overnight), and paraffin-embed the next day as per standard tissue processing procedures in Pathology lab.

Alternatively, if Pathology will be processing diagnostic FFPE tumor samples that will provide sufficient excess tissue for molecular analyses,

and tissues are fixed for less than 24 hours, then such samples may be used in lieu of punch biopsies.

**D) Extra tumor tissue-** If tissue requirements for categories A, B, and C are filled and excess tumor tissue is available, more 1-mm cores of fresh viable tissue for tissue culture are requested (up to 20 more). Such extra cores should be placed into tissue culture medium as in section A (above).

**Histological qualification of tumor samples-** The Pathologist will perform routine histological analysis of the diagnostic FFPE surgical tumor specimen. If the diagnostic tumor sample is found to have <50% tumor cellularity, the tumor samples procured for research will be considered non-evaluable, and this patient will need to be replaced.

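### The Letrozole-versus-baseline tests compare biopsy with surgical specimen in Arm B only, so any shift due to specimen type, handling or time is mixed with the Letrozole effect; Arm A pairs could serve as a partial control

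*Combined protocol and SAP*

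**What the plan says.** Secondary objective 1 (section 2.2) is: "To determine whether presurgical treatment with Letrozole suppresses IRS-1/PI3K/AKT pathway activation compared to baseline". Section 9.4 addresses it with a "paired t-test comparing IRS-1/PI3K/AKT pathway markers scored by IHC analysis of matching tumor samples from patients acquired A) at baseline (diagnostic biopsy") and "at surgery (post-Letrozole"). Only Arm B patients have a specimen of the second kind.

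The laboratory plan in section 5.5.2 has the same restriction: "Baseline (diagnostic core biopsy specimen) and post-Letrozole (surgical specimen) tumor samples will be sectioned and processed for IHC". It adds that "Pre- and post-Letrozole Ki67+ cell counts will be compared by t-test", without saying whether that test is paired. The stains it lists are ER, PR and Ki67. The pathway markers that section 9.4 relies on are not in that list.

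On tissue, inclusion criterion 3.1 applies to every patient: "Excess baseline biopsy tumor tissue sufficient to make three 5-micron sections must be available for molecular analyses as part of this study". Section 5.2.1 governs surgical specimens in both arms. It states that "All research samples must be acquired within 1.5 hours of tissue removal from the patient", and for the FFPE cores "fix in formalin (3 hours to overnight"), with suitable excess diagnostic FFPE tissue allowed instead. No handling rule is given for the diagnostic biopsy.

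Neither section 5.5.2 nor section 9.4 plans a biopsy-versus-surgery comparison in Arm A. The Arm A versus Arm B test in section 9.3 concerns the RAD001-induced change measured by immunoblot in surgical tissue, and does not use the biopsy.

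**The concern.** The two specimens in each Arm B pair differ in more than exposure to Letrozole. The first is a core needle or incisional biopsy taken for diagnosis. The second comes from a resection and may be sampled up to 1.5 hours after removal. Between them lie the 10-21 days of treatment and a screening period that section 5.1 allows to run up to 4 weeks. The protocol itself treats handling as relevant to tissue quality, since section 5.2.1 prefers minimal cold ischemia time.

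A one-sample test of paired differences estimates the sum of the Letrozole effect and any systematic biopsy-to-surgery shift. It cannot separate them. A shift that lowers the surgical score would be read as suppression, which is the result the study expects. A shift that raises it would hide real suppression. What is at stake is the interpretation of secondary objective 1 and of the Ki67 change, which section 5.5.2 links to a tumor's dependence on ER.

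**Working it through.** The plan gives no sample size, SD, effect size or power for the section 9.4 test, so it has no figure to reproduce.

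**Inputs from the documents.** Two-sided testing at 0.05 (section 9.5); Arm A n = 10 (section 5.2); Arm B n = 10, 14 or 30 (table in section 9.6).

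**Assumed.** A specimen shift of d SDs of the paired difference, shown as a range; normally distributed differences; a paired test for Ki67 as well.

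**Step 1: planned test with a true Letrozole effect of zero.** The t statistic is noncentral with n − 1 degrees of freedom and noncentrality δ = d√n. The rejection rate is P(|T| > t(0.975, n − 1)).

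| Arm B n | critical t | d = 0.3 | d = 0.5 | d = 1.0 |
|---|---|---|---|---|
| 10 | 2.262 | δ = 0.949: 14% | δ = 1.581: 29% | δ = 3.162: 80% |
| 14 | 2.160 | δ = 1.122: 18% | δ = 1.871: 41% | δ = 3.742: 93% |
| 30 | 2.045 | δ = 1.643: 36% | δ = 2.739: 75% | δ = 5.477: about 100% |

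At d = 0 the rate is 5% throughout. Rejections in the direction opposite to the shift are negligible (0.24% at most, at n = 10 and d = 0.3). A larger Arm B makes the problem worse, because the test detects the shift more reliably.

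**Step 2: between-arm contrast of the biopsy-to-surgery change.** With the same SD in both arms, the standard error in SD units is √(1/10 + 1/n_B), which is 0.447, 0.414 and 0.365 for n_B = 10, 14 and 30, with 18, 22 and 38 degrees of freedom. If the shift is equal in the two arms it cancels. In simulation with a common shift of 0.75 SD, the rejection rate was 0.049, 0.051 and 0.049.

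**Step 3: price in precision.** Effect detectable with 80% power, in SDs of the paired change:

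| Arm B n | paired test, Arm B only | Arm B minus Arm A |
|---|---|---|
| 10 | 1.00 | 1.33 |
| 14 | 0.81 | 1.21 |
| 30 | 0.53 | 1.05 |

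For a true effect of 1.0 SD with 10 per arm, power falls from 80% to 56%. For 0.5 SD with 30 in Arm B, it falls from 75% to 27%.

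**Step 4: if the shift is not equal in the two arms.** If the two arms' shifts differ by 0.5 SD (also an assumption), the between-arm test rejects 18.5% of the time at 10 versus 10 and 26.6% at 10 versus 30 when Letrozole does nothing.

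**The case against.** The strongest reply is that Arm A is not a clean control. It is enrolled first and not randomised, and Arm B opens only after Arm A's molecular analyses (section 5.2). The 4-week screening window is stated not to apply to Arm A (section 5.1), and Arm A has no treatment period, so its interval from biopsy to surgery is not set. It controls handling better than time, and step 4 shows that a difference in shift between arms would still mislead. This stands. A reader might infer that Arm A supplies equivalent untreated pairs and that the between-arm test should replace the paired one. The documents do not support the first inference, and the loss of precision in step 3 makes the second a trade-off rather than a correction.

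Tissue is also a real limit. Three baseline sections are guaranteed, and section 5.5.2 already names three stains. Using those sections for Ki67 and two phospho-AKT stains leaves none guaranteed for IRS-1, ER or PR.

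A reader might further infer that secondary objective 1 cannot be answered at all. That goes too far: the objective asks for change from baseline, and a paired test estimates that change. What is not supported is attributing the change to Letrozole. Nor do the documents show that handling lowers phospho-AKT or Ki67, so a bias toward suppression cannot be presumed.

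Finally, the analysis is secondary, in a self-described pilot. Section 5.5.2 gives its main goal as the association of RAD001-induced signaling changes with Ki67, and no listed objective is Letrozole's effect on Ki67. The primary RAD001 comparisons use cores from the same surgical specimen and are unaffected. All of this limits the weight of the point but does not remove it.

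**Conclusion.** The concern holds as a limit on interpretation. As written, sections 9.4 and 5.5.2 cannot separate Letrozole from specimen type, handling and time, and nothing else in the documents controls this comparison. The size depends wholly on a shift the documents do not give. Over the assumed range of 0.3 to 1.0 SD, the chance of a significant result with no drug effect is 14% to 80% at n = 10, 18% to 93% at n = 14 and 36% to about 100% at n = 30, against a nominal 5%. The direction of any shift is unknown.

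About 10 untreated Arm A pairs are available from tissue the protocol already requires. They can reduce the problem but not eliminate it: full correction would need the shift to be the same in both arms, which the design does not secure.

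**What to change.** Amend sections 5.5.2 and 9.4 as follows.

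- Stain the Arm A baseline and surgical pairs where tissue permits, giving priority to Ki67, phospho-AKT-S473 and phospho-AKT-T308. Stain them in the same batch as the Arm B pairs and score them masked to arm.
- Reconcile the section 5.5.2 stain list with the pathway markers needed for section 9.4, given three guaranteed baseline sections.
- Record and report the biopsy-to-surgery interval in both arms.
- Report the Arm B minus Arm A difference in change, with its confidence interval, alongside the within-Arm-B paired test.
- Describe the paired result as change from biopsy to surgery, and attribute it to Letrozole only if the between-arm contrast supports that.

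The cost is staining and scoring about 10 further pairs, plus revised wording. No extra patients or procedures are needed. The added contrast is imprecise, so it may be inconclusive, in which case the report should say that the change cannot be assigned to Letrozole.
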